23.2.1.2 Calculation of Baseline eDiary Assessments

Calculation of the eDiary baseline begins on the day of the Screening Visit.

In case of a 7-day extension of the Screening Period the last 21 days of the original 28 days Screening Period and the first 7 days of the extension will be used to calculate the baseline value. In case the extension is less than 7 days more days will be used from the Screening Period ending up with a total of 28 days.

When finding the baseline value for number of monthly attacks, the number of reported attacks will be scaled up to 28 days using (assuming that days with missing data are similar to the days with data):

$$28 * (\text{Reported number of attacks} / \text{Reported eDiary Days})$$

The average weekly number of attacks at baseline will be found by dividing the number of monthly attacks at baseline by 4:

$$28 * (\text{Reported number of attacks} / \text{Reported eDiary Days}) / 4$$

When finding the baseline number of times abortive medication was used the above formulas are used with *Reported number of attacks* replaced by *Reported number of times an abortive medication was taken*.

When finding the baseline values using the 5-point self-rated pain severity scale scores, three different formulas will be used. The **baseline monthly pain per attack** is found by:

Sum of reported pain across attacks/Number of reported attacks

The **baseline weekly pain per attack** equals the baseline monthly pain per attack.

The **baseline average attack related daily pain** is found by:

Sum of the average daily pain across days with data/Number of days with data

where days with 0 attacks will add a value of 0 to the nominator and count as a day in the denominator.

The **baseline monthly integrated measure of frequency and intensity of attack related pain** is found by:

$((\text{Sum of reported pain across days with data/Number of days with data}) * 28) / 4$

where days with 0 attacks will add a value of 0 to the nominator and count as a day in the denominator.

The **baseline weekly integrated measure of frequency and intensity of attack related pain** equals the baseline monthly integrated measure of pain.

23.2.1.3 Imputation of Missing Post-baseline eDiary Assessments

The strategy of imputation of missing values is given by:

1. For each weekly score in the periods with daily entries in the eDiary, prorating is used to impute any missing data when data have been observed for at least 4 days in a week, to have full weekly scores
2. For each monthly score, prorating is used to impute any missing data when data have been observed for at least 2 weeks in a month (after prorating weekly scores), to have full monthly scores

For a 7-day weekly period where the eDiary is completed in at least 4 out of 7 days, the number of attacks will be calculated using prorating:

$7 * (\text{Reported number of daily attacks/Reported eDiary Days})$

For participants where the eDiary is completed in 3 days or less, the 7-day weekly observation will be set to missing.

For a 4-week monthly period where the eDiary is completed in at least 2 out of 4 weeks, the number of attacks will be calculated using prorating:

$4 * (\text{Number of weekly attacks/Reported eDiary Weeks})$

For participants where the eDiary is completed in 1 week or less the 4-week monthly observation will be set to missing.

Use of abortive medication is prorated using the same criteria and formulas as above where *Reported number of daily attacks* is replaced by *Reported number of daily times an abortive medication was taken* and *Number of weekly attacks* is replaced by *Number of weekly times an abortive medication was taken*.

The severity of attacks is prorated using the same criteria as above using the same formulas as in section [23.2.1.2](#).

The derivation of the three pain scores can be seen in [Panel 5](#). When calculating the average attack related daily pain and the weekly integrated measure of frequency and intensity of attack related pain, a value of 0 will be added to the nominator and count as a day in the denominator for days/weeks with 0 attacks. Furthermore, the weekly pain per attack is not defined for days/weeks with 0 attacks.

Panel 5 Definitions of Post-Baseline Pain Scores

	Daily eDiary	Weekly eDiary
Average attack related daily pain	Sum of the average daily pain across days with data/number of days with data	NA
Weekly pain per attack	Sum of pain across attacks/number of attacks	Pain
Monthly pain per attack	Sum of the weekly pain per attack scores/ number of the weekly pain per attack scores	
Weekly integrated measure of frequency and intensity of attack related pain	(Sum of pain across days with data /days with data)*7	Pain*number of attacks
Monthly integrated measure of frequency and intensity of attack related pain	Sum of the weekly integrated measure of frequency and intensity of attack related pain scores/ number of the weekly integrated measure of frequency and intensity of attack related pain scores	

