3.4 Definition of a Month

A Month is referring to a 28-day period.

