
• To evaluate the efficacy of eptinezumab on health-related quality of life, health care resource utilization, and work productivity	
- Patient Global Impression of Change (PGIC) score at Weeks 4, 8, ..., 48- Change from Baseline in the Sleep Impact Scale (SIS) domain scores at Weeks 4, 12, 16, 24, 28, 36, 40, 48 - Exploratory endpoints:- Change from Baseline in the number of monthly attacks (Months 1, 2, ..., 12)- Change from Baseline in the pain per attack, as assessed using the 5-point self-rating pain severity scale (Months 1, 2, ..., 12)- Response: $\geq 30\%$ reduction from Baseline in the number of monthly attacks (Months 1, 2, ..., 12)- Response: $\geq 50\%$ reduction from Baseline in the number of monthly attacks (Months 1, 2, ..., 12)- Response: $\geq 75\%$ reduction from Baseline in the number of monthly attacks (Months 1, 2, ..., 12)- Response: 100% reduction from Baseline in the number of monthly attacks (Months 1, 2, ..., 12)- Change from Baseline in the monthly number of times an abortive therapy (oxygen and/or triptans, only oxygen, and only triptans) was used (Months 1, 2, ..., 12)- Change from Baseline in the weekly integrated measure of frequency and intensity of attack related pain, that is, the sum of the intensity (worst pain on a 5-point self-rating pain severity scale) for each attack during a week (Weeks 1, 2, 3, 4, 13, 14, 15, 16, 25, 26, 27, 28, 37, 38, 39, 40) or the intensity of attack related pain multiplied by the weekly number of attacks (Weeks 5, 6, ..., 12, 17, 18, ..., 24, 29, 30, ..., 36, 41, 42, ..., 48)- Use of triptans (Weeks 1-48)- Use of oxygen (Weeks 1-48)- Use of preventive medication (Weeks 1-48)- Sustained response: $\geq 75\%$ reduction from Baseline in the number of monthly attacks for any month, where all the subsequent months also had $\geq 75\%$ reduction from Baseline in the number of monthly attacks (Months 1, 2, ..., 12)- A maximum score of mild on the 5-point self-rating pain severity scale (Weeks 1, 2, ..., 48) - Secondary endpoints:- Change from Baseline in the EuroQol 5-Dimension 5-Level (EQ-5D-5L) score at Weeks 4, 16, 28, 40, and 48- Health Care Resources Utilization (HCRU) at Baseline and Weeks 4, 16, 28, 40, and 48- Change from Baseline in the Work Productivity Activity Impairment: General Health second version (WPAI:GH2.0) subscores (Absenteeism, Presenteeism, Work productivity loss, Activity impairment) at Weeks 4, 16, 28, 40, and 48

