13.5.9.3 Sensitivity Analyses to assess the impact of missing data regarding response

To assess the impact of only imputing data by prorating for response endpoints as described in section 13.5.6.2, LOCF and worst case imputations will be carried out for the endpoints regarding 75% response.

14 Safety

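### In the daily-diary months (1, 4, 7 and 10), a month with recorded attacks, or with only 8 of 28 days observed, can be scored as a 100% response

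*SAP*

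**What the plan says.** SAP Panel 2 (section 5) lists as exploratory "Response: 100% reduction from Baseline in the number of monthly attacks (Months 1, 2, ..., 12"). SAP 3.4 fixes the month length: "A Month is referring to a 28-day period".

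SAP 23.2.1.3 gives the derivation in two steps.

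- Week, in daily-diary periods: "prorating is used to impute any missing data when data have been observed for at least 4 days in a week". Below that, "For participants where the eDiary is completed in 3 days or less, the 7-day weekly observation will be set to missing". There is no exception for a short week in which attacks were recorded.
- Month: "For a 4-week monthly period where the eDiary is completed in at least 2 out of 4 weeks", the score is four times the weekly attacks divided by the number of reported weeks. With one week or none, the month is missing.

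SAP 13.5.6.2 applies this imputation, and no other, to the main 30%, 50%, 75% and 100% response summaries. It mentions LOCF and worst-case sensitivity analyses and refers to SAP 13.5.9.3 for details, where the scope is narrower: "LOCF and worst case imputations will be carried out for the endpoints regarding 75% response". The minimum-observation criteria in SAP 23.2.1.7 are for 3-, 6- and 12-month periods, not single months.

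**The concern.** Prorating is a defensible way to fill gaps in a mean count. It suits the event of having no attacks poorly, because zero scales to zero however little was observed. The rule also goes beyond an assumption about unseen days: it can contradict days that were seen. A participant whose diary shows attacks in a month can be tabulated as attack-free in that month.

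The SAP is stricter on a closely related endpoint. Remission (SAP 23.2.1.9) also requires at least four attack-free weeks but tolerates no more than one missing week. A month with two missing weeks can therefore be a 100% response without counting as a four-week remission. The baseline formula (SAP 23.2.1.2) uses all reported days, so baseline and post-baseline are handled differently.

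What is at stake is a descriptive rate in a single-arm, open-label trial. With no control arm to share the error, readers will take the attack-free percentage at face value.

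**Working it through.** The documents give no figure for this point, so there is none to reproduce. The check applies the rule as written.

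**Inputs from the documents.** Month of 28 days (SAP 3.4). At least 4 of 7 days for a week and 2 of 4 weeks for a month (SAP 23.2.1.3). Daily entries in Weeks 1–4, 13–16, 25–28 and 37–40 (SAP section 2), that is Months 1, 4, 7 and 10. At least 14 attacks in the 28-day Screening Period (SAP section 2), used as the baseline in the examples. Planned number 125 (protocol 5.1).

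**Formulas.** Week = 7 × attacks / days if at least 4 days are observed, otherwise missing. Month = 4 × (sum of weekly scores / weeks observed) if at least 2 weeks are observed, otherwise missing. For comparison, the SAP's own baseline formula over all reported days is 28 × attacks / days.

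| Case | Diary | Days seen | Attacks recorded | Weekly scores | Month under SAP | All-days score |
|---|---|---|---|---|---|---|
| A | Two weeks with 4 zero days, nothing else | 8 | 0 | 0, 0, –, – | 0 (100%) | 0 |
| B | Two full zero weeks; two weeks with 3 days, 1 attack per day | 20 | 6 | 0, 0, –, – | 0 (100%) | 28 × 6/20 = 8.4 (40.0% reduction) |
| C | Two weeks with 4 zero days; two weeks with 3 days, 1 attack per day | 14 | 6 | 0, 0, –, – | 0 (100%) | 28 × 6/14 = 12.0 (14.3%) |
| D | Three full zero weeks; one week with 3 days and 1 attack | 24 | 1 | 0, 0, 0, – | 4 × (0/3) = 0 (100%) | 28 × 1/24 = 1.17 (91.7%) |
| F | As D, with a fourth, attack-free day in the last week | 25 | 1 | 0, 0, 0, 1.75 | 4 × (1.75/4) = 1.75 (87.5%) | 28 × 1/25 = 1.12 (92.0%) |

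D and F differ by one extra attack-free diary day, and that day turns a 100% response into a non-response. B, C and D contradict recorded data. A does not; it shows how little observation is enough.

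**Size of the effect of unobserved days (assumptions, not document figures).** If attacks are Poisson with true mean m per 28 days and days are missing independently of attacks, P(no attack on d observed days) = exp(−m × d/28). For m = 2 this is 13.5% with 28 days, 36.8% with 14 and 56.5% with 8.

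Across participants, assume gamma-distributed means (average m of 10 to 30 per month, shape k of 0.5 to 0.7). Then P(0) = (1 + m × d/(28k))^(−k). Suppose 20% of months have only d days observed and the rest are complete. The inflation in percentage points is 20% × [P(0 in d) − P(0 in 28)].

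- m = 10, k = 0.5: P(0 in 28) = 21.8%. With 14 days, 30.2%, so +1.7 points (7.6% relative). With 8 days, 38.6%, so +3.4 points (15.4% relative).
- m = 30, k = 0.7: P(0 in 28) = 7.1%. With 14 days, 11.3%, so +0.9 points (12.0% relative). With 8 days, 16.4%, so +1.9 points (26.2% relative).

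Over the grid the range is about 0.9 to 1.7 points (14 days) and 1.9 to 3.4 points (8 days). For scale, the 95% CI half-width at N = 125, 1.96 × √(p(1 − p)/125), is 4.5 points at p = 7.1% and 7.2 points at p = 21.8%.

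**Size of the effect of discarded attacks.** This cannot be computed. It depends on how often a short week contains attacks while at least two other weeks are attack-free, and the documents give no post-baseline diary missingness.

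**The case against.** The case for leaving the plan alone has real content. The endpoint is exploratory, nothing is formally tested and the primary objective is safety. Diary compliance is checked at every visit and phone contact (protocol 8.1), and SAP section 12 tabulates weekly completeness with the percentages having 4, 5, 6 and 7 days, so poor completion will be visible. The modelled inflation is smaller than the sampling error of the rate. All of this stands and limits the importance of the point. None of it prevents the misclassification: a completeness table does not show which responders had recorded attacks.

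Three stronger readings are tempting and should not be drawn.

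- *Poorer compliance always raises the rate.* The documents do not support this. Below two observed weeks the month becomes missing, and an attack-free short week is discarded too, which can make a zero month missing. The single-month denominator is not stated; if it is the FAS, missing months lower the rate.
- *The modelled inflation measures the discarded attacks.* It does not. Those figures come only from unobserved days under assumed missingness, and the 20%, the means and the shapes have no source in the documents.
- *All months share the 3-day rule and the 8-day minimum.* They apply only where the diary is daily. In the other eight months no partial week is dropped for having too few days; the weakness there is that half the weekly entries are enough.

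The mean-count analyses are not challenged here.

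**Conclusion.** The point holds with this scope. In Months 1, 4, 7 and 10 the rule as written can classify a month with recorded attacks, or with 8 of 28 days observed, as a 100% response; in the other months two of four weekly entries suffice. Nothing in SAP 13.5.6.2, 13.5.9.3 or 23.2.1.7 prevents it. Among months that remain scored, discarding recorded attacks can turn a non-response into a response but never the reverse, so its direction is certain even though its frequency is unknown. The effect of unobserved days is roughly 1 to 3 percentage points, given gamma-Poisson attack counts, attack-independent missing days and 20% incomplete months. If missing days tend to be attack-free, that part is smaller. The consequence is confined to descriptive responder rates; no test and no primary safety result changes. The correction is worth making because it is small and the present rule can contradict the diary.

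**What to change.** 1. In SAP 23.2.1.3 and 23.2.1.7, state that for months and periods meeting the existing minimum-observation rule, any attack recorded on a diary day kept in DPS3 rules out 100% response, including days in weeks with three or fewer completed days. With this rule, cases B, C and D become non-responses.
2. State that months below the minimum stay missing whether or not an attack was recorded. Otherwise incomplete months would be classified by their outcome: an attack would make the month a non-response, while the same month without one stayed missing.
3. In SAP 13.5.9.3, extend the worst-case analysis to 100% response, with months that have missing weeks or days counted as non-response. This addresses case A, which step 1 leaves unchanged.
4. Report the number of days or weeks observed beside the rate. Restricting to months with all four weeks observed would not be enough in daily-diary months, since four weeks of four days (16 of 28) would still qualify.

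The cost is SAP wording and a small amount of extra programming, with no new data. The downside is a slightly lower 100% response rate.

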3.1 Definition of Baseline

For the efficacy endpoints based on the eDiary, e.g. the number of cluster headache attacks, the data collected during the first 28 days of the Screening Period will be used to calculate the baseline value for the endpoints. In case of a 7-day extension of the Screening Period, the last 21 days of the original 28 days Screening Period and the first 7 days of the extension will be used to calculate the baseline value (if the extension is less than 7 days the days used prior to the extension should be changed accordingly ending up with a total of 28 days). Furthermore, in case of re-screening, the baseline values will be calculated based on the first 28 days of the re-screening period. See section [13.5.1.1.1](#) and chapter [23](#) for handling of missing data.

For the endpoints not based on the eDiary, the baseline value is the value captured either during the Screening Visit or at the Baseline Visit prior to the infusion, whichever is later.

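### Pain per attack is weighted by attacks at baseline but by weeks afterwards, so an unchanged daily diary can show a change

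*SAP*

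**What the plan says.** SAP chapter 5, Panel 2 lists among the exploratory endpoints "Change from Baseline in the pain per attack, as assessed using the 5-point self-rating pain severity scale", for each of Months 1 to 12. SAP 13.5.6.1 analyses it by MMRM, adds period contrasts up to Months 1-12, and asks for additional Weeks 1-2 and Weeks 1-4 estimates of the weekly score. It also says that monthly scores are built from weekly scores.

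- **Baseline.** Under SAP 3.1, "the data collected during the first 28 days of the Screening Period will be used to calculate the baseline value for the endpoints". SAP 23.2.1.2 defines monthly pain per attack as "Sum of reported pain across attacks/Number of reported attacks". The weekly baseline "equals the baseline monthly pain per attack".
- **After baseline.** In Panel 5 of SAP 23.2.1.3, a week with daily entries is scored as total pain over that week's attacks. A week with a weekly entry is scored as its single Pain rating. The monthly score is "Sum of the weekly pain per attack scores/ number of the weekly pain per attack scores".
- **Attack-free weeks.** SAP 23.2.1.3 adds: "Furthermore, the weekly pain per attack is not defined for days/weeks with 0 attacks".
- **Cross-references.** The same section states "The severity of attacks is prorated using the same criteria as above using the same formulas as in section" 23.2.1.2. It then says "The derivation of the three pain scores can be seen in" Panel 5.

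**The concern.** The change score subtracts one kind of average from another. The baseline pools all attacks in 28 days. The post-baseline month gives a week with 1 attack the same weight as a week with 10. If a patient's busier weeks are also the more painful ones, the pooled baseline lies above the mean of the weekly scores, and the difference reads as improvement. If the busier weeks are milder, it reads as worsening.

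The trial has one arm, so no control group cancels a shift in definition: the change from Baseline is the result. Baseline as a covariate in the MMRM does not remove an average offset, because the outcome is still measured against the pooled value.

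**Working it through.** The documents give no figure for this endpoint, so there is none to reproduce. The check applies both rules to the same 28-day daily diary.

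**Formulas.** Let n be attacks in a week and p the mean pain of that week's attacks.

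- Baseline rule (23.2.1.2): sum(n × p) / sum(n).
- Post-baseline rule (Panel 5): mean of p over weeks with n > 0.
- Difference, post-baseline minus baseline: −Cov(n, p) / mean(n), using the population covariance over weeks with attacks.

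This is zero only when the covariance is zero, for example with equal weekly counts or constant weekly pain.

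**Constructed diaries**, each meeting the 14-attack entry minimum on the 0-4 scale:

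| Attacks by week | Weekly mean pain | Baseline rule | Panel 5 rule | False change |
|---|---|---|---|---|
| 4/4/4/4 | 2/3/4/3 | 48/16 = 3.00 | 12/4 = 3.00 | 0 |
| 7/5/3/5 | 3.5/3/2.5/3 | 62/20 = 3.10 | 12/4 = 3.00 | −0.10 |
| 10/10/2/1 | 4/4/3/3 | 89/23 = 3.87 | 14/4 = 3.50 | −0.37 |
| 10/10/2/1 | 3.5/3.5/2/2 | 76/23 = 3.30 | 11/4 = 2.75 | −0.55 |
| 2/2/2/10 | 3/3/3/2 | 38/16 = 2.375 | 11/4 = 2.75 | +0.375 |
| 8/6/0/0 | 4/2/–/– | 44/14 = 3.14 | 6/2 = 3.00 | −0.14 |

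The identity agrees. The second row has covariance 0.5 and mean 5, giving −0.10. The third has covariance 2.125 and mean 5.75, giving −0.37. The second row is stylised, because 7 or 3 whole-number ratings cannot average exactly 3.5 or 2.5. Weekly pain totals of 24/15/8/15 give 3.02 against 3.10 (−0.08), and 25/15/7/15 give 2.98 against 3.10 (−0.12).

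**Upper limit.** With attacks in all four weeks and N their total, the absolute false change is at most (range of weekly mean pain) × 0.5 × sum|n/N − 1/4|. Per 1-point range this is:

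- 0.07 for 4/4/3/3
- 0.10 for 7/5/3/5
- 0.20 for 8/6/4/2
- 0.37 for 10/10/2/1

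**Group average, on assumed inputs.** A simulation assumed about 7 attacks a week, a log-SD of 0.5 for the weekly rate and a between-week pain SD of 0.5. The mean false change was 0.00, −0.05 and −0.10 points for rate-pain correlations of 0, 0.3 and 0.6. The per-patient SD was about 0.15. None of these inputs comes from the documents.

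**Weeks 1-2 and 1-4.** These estimates also average weekly scores equally against the pooled baseline, so the same mismatch of definitions applies. They are contrasts of MMRM week means, and the identity above does not give their size.

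**The case against.** The strongest reply is that SAP 23.2.1.3 sends post-baseline severity back to the 23.2.1.2 formulas. Read literally, that would pool attacks after baseline too, and the mismatch would vanish in the daily-diary months. But that sentence concerns prorating, the next one gives Panel 5 as the derivation, and 13.5.6.1 builds months from weeks. Panel 5 is the better reading. What stands is that the two sentences do not sit well together and need rewording.

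A second reply is that pooling matches the name pain per attack better, so the post-baseline score should move instead. That is also a valid repair: total pain over total attacks in the daily-diary months gives exactly zero change for an unchanged diary. Re-deriving the baseline has the advantage of fitting scores that the SAP builds from weeks, and it also serves the weekly estimates.

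Third, the larger examples are deliberately uneven. Diagnosis requires severe or very severe pain (Protocol 9.1.2, Panel 4), so a wide range of weekly pain at screening may be uncommon. This is fair, and it is why the size is given as a limit and not as an expected value.

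Finally, in the weekly-diary months one rating per week replaces ratings of individual attacks. No reweighting of baseline cures that. This is correct, and it should be declared.

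**Conclusion.** The mismatch is real as the SAP is written, taking Panel 5 as governing. An unchanged daily diary gives a non-zero monthly change whenever weekly attacks and weekly pain are correlated. Under the simulation's assumptions the average effect is at most about 0.1 point. In uneven individual diaries it can pass 0.3 point in either direction. The true size and sign cannot be derived from the documents.

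The importance is low. The score is exploratory, SAP 13.2 rules out formal testing, the primary objective is safety, and the secondary average daily pain endpoint uses the same formula before and after baseline. The point is worth considering because the correction is cheap.

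**What to change.** 1. In SAP 23.2.1.2, derive baseline pain per attack as the mean of the weekly pain-per-attack scores over the four screening weeks (days 1-7, 8-14, 15-21 and 22-28 of the 28-day window in SAP 3.1). Apply the 4-of-7-day rule, leave attack-free weeks undefined, and use this value for both the weekly and the monthly change scores. Identical daily entries then give zero monthly change by construction.
2. Reword the cross-reference in SAP 23.2.1.3 so that Panel 5 clearly governs the derivation.
3. State the remaining limitation. Weekly entries cover 48 − 16 = 32 of 48 weeks, that is 8 of 12 months, so only Months 1, 4, 7 and 10 are like-for-like with baseline.

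This is feasible. Inclusion criterion 11 (Protocol 5.3) requires entries on at least 24 of 28 days, so at most 4 are missing. A week fails the rule only if at least 4 of its 7 days are missing, so at most one screening week can be lost. The price is that the attacks observed in that week drop out of the baseline.

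The cost is SAP wording and one derivation from daily screening data already collected. No new data are needed.
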